- If study dosing stopping criteria are met: In addition to the individual patient instruction above, no further patients will be dosed within the cohort currently being investigated and no further dose escalation will occur; patients who have been dosed will be followed up as per protocol.

The symptoms in [Table 6](#) have been classified as objective and subjective endpoints as follows:

Objective Endpoints: Fever, Diarrhoea, Vomiting, Hypotension

Subjective Endpoints: Headache, Chills, Nausea, Arthralgia, Myalgia

Based on the above classification four possible outcomes have been defined where dosing would be stopped, as described in [Table 6](#):

Table 6 Stopping Criteria for CRS-Adverse Events

Scenario	NCI-CTC Scores	Individual Subject Criteria
I	2 objective endpoints \geq grade 2 OR Fever, vomiting, or diarrhoea \geq grade 2 persisting >48 hours despite treatment	Stop treatment
II	1 objective endpoint \geq grade 2 AND 
 • 2 subjective endpoints (except chills) \geq grade 3 OR • 1 subjective endpoint \geq grade 3 and Chills \geq grade 2 	Stop treatment
III	Three subjective endpoints \geq grade 3 (except if one subjective endpoint is Chills, which only needs to be \geq grade 2)	Stop treatment
IV	1 objective endpoint \geq grade 4	Stop treatment
Study Dosing Stopping Criteria: 
 • If ≥ 3 subjects on otelixizumab treatment within a cohort meet individual Stopping Criteria I-III detailed above. 
Or
 
 • If 1 subject on otelixizumab treatment within a cohort meet individual Stopping Criteria IV. 		

Note: in order to meet individual stopping criteria, the reported objective or subjective endpoints must be of different types during one 24 hour dosing period for any of the scenarios involving more than one endpoint.

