5.4. Blinding

This will be a single blind study where the patients will not be aware of the treatment they receive. All staff including site personnel, CRO and sponsor team members will be unblinded. However, the randomisation code will be restricted to the pharmacist preparing the infusions.

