7.1.5. Cytokine Release Syndrome Adverse Events

CRS is a well-known consequence of anti-CD3 therapy when administered via intravenous injection or infusion and therefore any CRS AEs experienced during the dosing period will be assessed against the grading system shown in [Table 5](#). This grading system has been developed using NCI Common Terminology Criteria for Adverse Events (CTCAE) v.4 ([Table 5](#)) by selecting AEs that are specifically thought to be associated with cytokine release syndrome. Pre-specified CRS individual patient and study dosing stopping criteria are shown in [Table 6](#). The symptoms in [Table 6](#) have been classified as objective and subjective endpoints as follows:

- **Objective Endpoints:** Fever, Diarrhoea, Vomiting, Hypotension
- **Subjective Endpoints:** Headache, Chills, Nausea, Arthralgia, Myalgia

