2.2. Study Objective(s) and Endpoint(s)

Primary	
Primary Objectives (Safety)	Primary Endpoints (Safety)

 To assess the effect of a single course of otelixizumab treatment on the acute and long term safety and tolerability of otelixizumab in NOT1DM patients. 	
 Incidence of adverse events (AEs) particularly those related to Cytokine release syndrome (CRS). Epstein-Barr virus (EBV) reactivation over Day 21 to Month 24. Changes in laboratory values, electrocardiograms (ECGs) and vital signs over Day 14 to Month 24.
Secondary	
Secondary Objectives (Pharmacokinetic)	Secondary Endpoints (Pharmacokinetic)

 To assess the pharmacokinetics of repeat dose administration of otelixizumab over 14 days in NOT1DM patients. 	
 Free serum otelixizumab concentrations over Days 1-14 and summary PK parameters.
Secondary Objectives (Efficacy)	Secondary Endpoints (Efficacy)

 To assess the effect of a single course of otelixizumab treatment on the rate of decline of pancreatic β-cell function over 24 months in NOT1DM patients. 	
 Change from baseline in C-peptide and glucose AUC (0-120) after a Mixed Meal Tolerance Test at Month 3, 6, 12, 18 and 24.

 To assess the effect of a single course of otelixizumab treatment on the rate of decline of C-peptide response and insulin sensitivity of β-cell function determined after a hyperglycemic clamp over 24 months in NOT1DM patients. 	
 Change from baseline in C-Peptide and glucose AUC hyperglycemic phase [H60 to H140 minutes] and insulin sensitivity (IS) index after a hyperglycemic clamp at Months 6 and 24.

 To assess the effect of a single course of otelixizumab treatment on exogenous insulin use for otelixizumab over 24 months in NOT1DM patients. 	
 Change from baseline in mean daily insulin use over 7 consecutive days during the week preceding all visits and phone calls.

 To assess the effect of a single course of otelixizumab treatment on glycaemic control over 24 months in NOT1DM patients. 	
 Change from baseline in HbA1c level. Body weight Day -1, Months 12-24. Hypoglycemic & hyperglycemic events over Months 1-24.

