AE = Drug-related	➤ If relationship is marked 'YES' on eCRF OR value is missing.								
Adverse Events : CRS and Clinical Symptoms of Mononucleosis Definition									

 The current MedDRA version at time of database lock will be used for coding of AE's. AEs considered to be related to CRS during the first 14 days post first dose will be determined by medical expert review conducted by the GSK team. For reporting of clinical symptoms of mononucleosis, the following AE's will be extracted based on Preferred Term. In addition, other terms maybe included at the time of reporting. 									
	
  
 Reporting	Preferred Term	Verbatim Terms	
   
 Clinical	Fatigue	Feeling tired & Low energy	
  
	Reporting	Preferred Term	Verbatim Terms	Clinical	Fatigue	Feeling tired & Low energy		
Reporting	Preferred Term	Verbatim Terms							
Clinical	Fatigue	Feeling tired & Low energy							

Adverse Events		
General		
Symptoms of Mononucleosis	Malaise	Feeling unwell
	Myalgia	Joint and muscle pain & Flu like symptoms
	Oropharyngeal pain	Sore throat, throat pain
	Lymphadenopathy	Swollen glands
	Pyrexia	High temperature, Feeling hot and cold & Shivering

Laboratory Parameters

 • All BLQ values will be imputed with $\frac{1}{2}$ LLOQ. • All ALQ values will be imputed with the ALQ + [smallest positive number with the same number of decimal places as the ALQ is reported with] • Values reported as < x are assumed to have an LLOQ of x. • Values reported as > x are assumed to have an ALQ of x.

EBV				

 EBV Serology: 
 Categories (negative, positive) will be derived from absolute IgG and IgM values according to a worst case approach from absolute virus results 				
	QUEST Classification of INDEX	Quest classification of U/ml	BDR Classification of AE/mL	Unified Classification
IgG	< OR = 0.90 NEGATIVE 0.91 - 1.09 EQUIVOCAL > OR = 1.10 POSITIVE		negative : <20 positive : 20 or more	NEGATIVE POSITIVE POSITIVE
IgM	< OR = 0.90 NEGATIVE 0.91 - 1.09 EQUIVOCAL > OR = 1.10 POSITIVE	negative: <36 positive: 36 or more	negative : <20 weakly positive : 20-40 positive : 40 or more	NEGATIVE POSITIVE POSITIVE POSITIVE

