11.10.5. Safety Tables

Safety: Tables					
No.	Population	IDSL / TST ID / Example Shell	Title	Programming Notes	Deliverable [Priority]
AE					
2.01.	Safety	AE13	Adverse Event Overview	Split as described in Section 11.3	FA (SAC)
2.02.	Safety	AE15	Summary of All Adverse Events by System Organ Class and Preferred Term	Split as described in Section 11.3 Add a "Any Event" category for each SOC even if not in shell	FA (SAC)
2.03.	Safety	AE15	Summary of Drug-Related Adverse Events	Split as described in Section 11.3 Add a "Any Event" category for each SOC even if not in shell	FA (SAC)
2.04.	Safety	AE16	Summary of Serious Adverse Events by System Organ Class and Preferred Term	Split as described in Section 11.3	FA (SAC)
2.05.	Safety	AE1	Summary of AEs Leading to Permanent Discontinuation of Study Drug or Withdrawal from Study	Do not split this output by phase	FA (SAC)
2.06.	Safety	AE5	Summary of All Adverse Events by Maximum Grade by System Organ Class and Preferred Term	Split as described in Section 11.3	FA (SAC)
2.07.	Safety	AE5	Summary of Drug-Related Adverse Events by Maximum Grade by System Organ Class and Preferred Term	Split as described in Section 11.3	FA (SAC)
Cytokine Release Syndrome					

2.08.	Safety	AE15	Summary of Adverse Events - Cytokine Release Syndrome Induced Symptoms	
 • Definition of Cytokine Release Syndrome in Section 11.5.3 • Overall only, not split by study phase. 	FA (SAC)
Epstein-Barr Virus					
2.09.	Safety	AE15	Summary of Adverse Events Considered to be Potentially Associated with EBV Reactivation	
 • Clinical Symptoms of Mononucleosis AE Terms to include are in Section 11.5.3 • Overall only not split by study phase. 	FA (SAC)
2.10.	Safety	Non-Standard SAFE_T3	Summary of categorical values of Epstein-Barr Virus (Serology: IgG & IgM)	
 • Categories (negative, positive) to be derived from absolute values according to a worst case approach as described in Section 11.5.3 	FA (SAC)
2.11.	Safety	Non-Standard SAFE_T2	Summary of Epstein-Barr Viral Load (PCR)	
 • Geometric Means 	FA (SAC)
2.12.	Safety	Non-Standard SAFE_T4	Categorical Summary of Epstein-Barr Viral Load (PCR)		FA (SAC)

Labs

2.13.	Safety	LB1	Summary of Laboratory Values	
 Order parameters alphabetically. BY Labtype (1. Chemistry, 2. Haematology) 	FA (SAC)

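### The CRS adverse events in SAP Table 2.08 rest on sponsor judgement with no written criteria or masking, and no planned display ties them to the protocol's Table 5 grades or Table 6 stopping rule

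*SAP*

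**What the plan says.** The primary endpoint in protocol Section 2 and SAP 2.2 is the incidence of adverse events, with CRS-related events picked out for emphasis.

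Protocol 5.3.1 names nine CRS symptoms. Four are objective ("Fever, Diarrhoea, Vomiting, Hypotension") and five are subjective (headache, chills, nausea, arthralgia, myalgia). Table 5 grades them, and Table 6 builds the individual and cohort stopping rules on those grades. Protocol 7.1.5 adds that "any CRS AEs experienced during the dosing period will be assessed against the grading system shown in" Table 5.

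For the final report, SAP 11.5.3 says that CRS-related events "during the first 14 days post first dose will be determined by medical expert review conducted by the GSK team". It lists no preferred terms, states no criteria, does not mask the reviewers and does not date the review. The next bullet of the same section gives mononucleosis symptoms a preferred-term list, although an open one.

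Two displays depend on the rule: Table 2.08, "Summary of Adverse Events - Cytokine Release Syndrome Induced Symptoms", and Listing 21. On blinding, protocol 5.4 says "All staff including site personnel, CRO and sponsor team members will be unblinded". Its next sentence confines the randomisation code to the pharmacist who prepares the infusions.

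**The concern.** Headache, nausea, chills and myalgia are nonspecific and can occur on placebo. If the person deciding whether a headache is CRS knows the arm and the dose, the same report can be counted in one group and left out in another. The dose comparison of CRS is a main product of this escalation study, and Table 2.08 is the table a reader will turn to for it.

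Without written criteria, a reader cannot repeat the selection or judge whether it was even-handed. Without Table 5 grades or a Table 6 count, the reported CRS figures also cannot be matched to the rule under which cohorts were allowed to proceed or were stopped.

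**Working it through.** **Inputs.** Nine symptoms: 4 objective + 5 subjective = 9 (protocol 5.3.1). Eight active and two placebo patients per cohort, and a Beta(1, 1) prior (protocol 9.2.1). Three reported dose levels and pooled placebo (SAP 5.1).

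**The plan's own figure.** Protocol Table 10 is the only design figure tied to CRS. With r events in 8 patients the posterior is Beta(1 + r, 9 − r).

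- r = 3: 95% interval 0.137 to 0.701 and P(rate > 0.375) = 0.546. The protocol prints 0.14 to 0.70 and 0.55.
- r = 2: 0.075 to 0.600 and 0.282. The protocol prints 0.07 to 0.60 and 0.28.
- All nine probabilities in the table agree with the printed values to within 0.01.

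**Effect of reclassifying one patient.** The step in incidence is 100 × 1/n percentage points.

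- Active arm as planned, n = 8: 100/8 = 12.5 points.
- Pooled placebo, assumed n = 2 × 3 = 6: 100/6 = 16.7 points.
- The documents do not give the numbers actually dosed. SAP 2.3 records that stopping criteria were met in Cohort 3, and protocol 5.3.1 and 5.3.2 halt further dosing when that happens, so the 27 mg and placebo groups may be smaller. By way of range, n = 5 would give 100/5 = 20.0 points and n = 4 would give 100/4 = 25.0.

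On the Table 10 scale, with assumed counts, one extra event in 8 moves P(rate > 0.375) as follows: from 1/8 to 2/8, 0.09 to 0.28; from 2/8 to 3/8, 0.28 to 0.55; from 3/8 to 4/8, 0.55 to 0.78. This shows only how sensitive so small a group is. The expert review does not feed the stopping rule.

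**What the listed displays show (SAP 11.10).**

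| Display | CRS selection | Grade | Dosing phase |
|---|---|---|---|
| Table 2.08 (shell AE15) | Sponsor review | No | No, overall only |
| Listing 21 | Sponsor review | Table 5 not specified | Not specified |
| Table 2.06 (shell AE5) | None, all AEs | Maximum grade, scale not stated | Yes |

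Table 2.06 gives graded counts by preferred term in the dosing phase without any sponsor selection, but the SAP does not say that the grades are those of Table 5. It also cannot yield the Table 6 count. Scenarios that need more than one endpoint require different symptom types within one 24-hour dosing period, and counts by term lose that within-patient combination. Table 2.05 and Listings 03 and 19 will show who stopped treatment or withdrew, but are not specified to show which scenario was met. No listed table gives the number of patients per dose who met scenarios I to III or IV.

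**The case against.** The strongest reply is that the protocol never made the nine symptoms the analysis definition. They serve grading and stopping, and protocol 9.3.3 sends the detail of CRS analysis to the analysis plan. This stands. A reader might infer that the SAP replaced a protocol definition and that its statement of no changes in Section 2.1 is therefore wrong. The documents do not support that. What remains is that the SAP accepted the task and supplied no criteria.

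A reader might also treat 14 days against six dosing days as an error in itself. Protocol 3.1, however, follows CRS from dosing until symptoms resolve, so a longer window has a basis. The protocol's own windows differ and should be reconciled.

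A third tempting inference is that the whole primary safety result is biased. It is not: Tables 2.01 to 2.07 present adverse events without CRS selection, the analysis is descriptive, and only the CRS subset is exposed.

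Nor do the documents say that the review is made after the data are seen. SAP 2.3 records the stop in Cohort 3 and SAP Section 4 cites a document dated 25 July 2018, so early events already existed when this SAP was written. The timing of the review itself is not stated.

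On masking, the pharmacist restriction in protocol 5.4, and the reference in SAP 4.1 to a deviation review before unblinding, sit badly with the statement that all staff are unblinded. No text, however, masks the CRS reviewers. The direction of any bias is unknown: generous attribution on active drug would overstate its toxicity.

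Finally, a fixed symptom list has faults of its own. Protocol Appendix 4 asks for the diagnosis to be recorded rather than its symptoms, so a bare nine-term list would miss an event entered as cytokine release syndrome. Site staff who elicit and grade symptoms are also described as unblinded. Both points stand and shape the fix.

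**Conclusion.** The concern holds for the CRS subset. Table 2.08 and Listing 21 depend on a sponsor judgement with no written terms, criteria or masking, made by a team that the protocol describes as unblinded. No listed display connects that subset to Table 5 grades or to the Table 6 rule.

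One reclassified patient is worth 12.5 points in an active arm if eight were dosed, and 16.7 points in placebo if six were pooled. The steps are larger if Cohort 3 was cut short. These figures measure how far one judgement can move the result; they are not evidence that bias has occurred.

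The conclusion assumes that no separate document sets criteria or masking for the review; the SAP refers to none. It calls for a cheap improvement, not a finding that the safety results are unsound or that the protocol was breached.

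**What to change.** - Add a CRS table based on a fixed MedDRA preferred-term list covering the nine Table 5 symptoms plus diagnosis-coded terms such as cytokine release syndrome and infusion related reaction. Use events with onset in the dosing period, shown by maximum Table 5 grade and dose. State which dosing window applies, since SAP Section 7 ends it on the day of the last dose and SAP 11.3.1 one day later.
- Add the number of active patients per dose who met Table 6 scenarios I to III, and IV, with the numbers actually dosed as denominators.
- Keep the 14-day expert review alongside. Write its criteria into the SAP, mask reviewers to treatment where feasible, and flag in Listing 21 every event on which the two approaches differ.
- Reconcile the two statements in protocol 5.4 on who is unblinded and who holds the randomisation code.

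The cost is SAP wording, a term list, one added table and one added count. Protocol 5.3.1 and 7.1.5 already require the grading. The Table 6 count assumes that grades and onset times were recorded closely enough to place symptoms within a 24-hour dosing period. No clinical rule changes. The downside is that a fixed list will count some incidental symptoms, which comparison with the expert review will show. Unblinded reporting at the sites remains a limitation that no analysis table removes.

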16. Significant and/or active disease in any body system likely to increase the risk to the subject or interfere with the subject's participation in or completion of the study. Examples of significant diseases include, but are not limited to, coronary artery disease, congestive heart failure, uncontrolled hypertension, renal failure, emphysema, history of bleeding peptic ulcers, history of seizure(s), addiction to illicit drugs, and alcohol abuse.
17. Clinically significant (based on Investigator's discretion in consultation with the Medical Monitor if second opinion required) abnormal laboratory values during the screening period, other than those due to T1DM. A clinically significant abnormal value will not result in exclusion if, upon retest, the abnormality is resolved or becomes clinically insignificant.
18. Positive EBV capsid Ab IgM in absence of a positive EBV EBNA Ab IgG

19. EBV viral load of $>10,000$ copies per 10^6 peripheral blood mononuclear cells (PBMCs) as determined by quantitative polymerase chain reaction (qPCR)..
20. IgG negative for EBV.
21. A positive result on a test for syphilis; and if result of the first test is positive, then a confirmatory test using another method will be performed.
22. Have used any atypical antipsychotic drug (e.g., risperidone [Risperdal], quetiapine [Seroquel], or clozapine [Clozaril]) within the 30 days before signing the ICF.
23. Have previously received orelizumab or any other anti CD3 monoclonal antibody, e.g., OKT3 (muromonab or Orthoclone), ChAglyCD3, or hOKT3 γ 1 (ala ala), and are not willing to refrain from using any such antibody for the planned duration of study participation (2 years after the last dose of study drug).
24. Previous or current exposure to biologic cell-depleting therapies (e.g. anti-CD11a, anti-CD22, anti-CD20, anti-BLyS/BAFF, anti-CD3, anti-CD5, anti-CD52) including investigational agents, and planning to use any such antibody for the planned duration of study participation (2 years after the last dose of study drug).
25. Predisposition to thromboembolic disease, or thromboembolic event (excluding superficial) in the past 12 months.
26. Is currently receiving corticoid treatment or has received systemic corticoid treatment within a month of screening.
27. History of Graves disease
28. Prior allergic reaction, including anaphylaxis, to any human, humanised, chimeric, or rodent antibody.

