5.3.2. EBV Stopping Criteria

Three parameters as described in [Table 7](#) will be used to assess EBV reactivation at a patient level to determine dose escalation:

Table 7 Parameters used to Assess EBV Reactivation

Parameter	Criteria
Clinical Symptoms of Mononucleosis	Fever, fatigue, malaise, myalgia, pharyngodynia, lymphadenopathy
Change in Viral Load	EBV by PCR more than 10,000 copies per 10 ⁶ peripheral blood mononuclear cells
Change in Serology	Emergence of IgM for EBV on otherwise EBV-IgG positive patients

Table 8 shows the possible combinations of the three EBV parameters that will be used to assess whether the patient has clinical EBV reactivation for the purpose of the stopping criteria. The assessment will be conducted for each subject at approximately 6 weeks post first active dose.

Table 8 Assessment of EBV Reactivation

Clinical Signs of Mononucleosis	Serology	Virology	EBV Reactivation
+	-	-	NO*
+	+	+	YES
+	+	-	YES
+	-	+	YES
-	-	-	NO
-	+	+	NO
-	+	-	NO
-	-	+	NO

*Other causes of mononucleosis should be checked

There will be ongoing reviews of safety data throughout the trial progression and on completion of each cohort.

[figure not shown]
If $\geq 3/8$ patients on active treatment within a cohort develop symptoms of clinical EBV reactivation as described above, the dosing will be stopped and no further dosing will be carried out on any other patients; patients who have been dosed will be followed up as per protocol.

Patient history will be assessed for symptoms of infectious mononucleosis, and spontaneous AE reporting will be implemented for assessing clinical EBV reactivation.

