Summary (Absolute and Change from Baseline) of Epstein-Barr Virus (Viral Load: PCR)

Summary: Change from Baseline

ETC

Programming Notes : [1] For applicable endpoints, include parameter as either a BY parameter or as first column in the table

Example : SAFE_T3
 Protocol : OTX116505
 Population : Safety

Table X.XX
 Summary of Categorical values of Epstein-Barr Virus (Serology:IgG & IgM)

Parameter	Visit	Treatment	N	n	Number of Subjects (%)					
					Absolute Values		Change from Baseline			
					Positive	Negative	Positive-Positive	Positive-Negative	Negative-Positive	Negative-Negative
Epstein-Barr IgG Antibody	Screening	Placebo	XX	XX	XX (%)	XX (%)				
		OTX 9 mg	XX	XX	XX (%)	XX (%)				
		OTX 18 mg	XX	XX	XX (%)	XX (%)				
		OTX 27 mg	XX	XX	XX (%)	XX (%)				
	Day -1	Placebo	XX	XX	XX (%)	XX (%)				
		OTX 9 mg	XX	XX	XX (%)	XX (%)				
		OTX 18 mg	XX	XX	XX (%)	XX (%)				
		OTX 27 mg	XX	XX	XX (%)	XX (%)				
	Day 6	Placebo	XX	XX	XX (%)	XX (%)	XX (%)	XX (%)	XX (%)	XX (%)
		OTX 9 mg	XX	XX	XX (%)	XX (%)	XX (%)	XX (%)	XX (%)	XX (%)
		OTX 18 mg	XX	XX	XX (%)	XX (%)	XX (%)	XX (%)	XX (%)	XX (%)
		OTX 27 mg	XX	XX	XX (%)	XX (%)	XX (%)	XX (%)	XX (%)	XX (%)

Example : **SAFE_T4**
 Protocol : OTX116505
 Population : Safety

Table X.XX
 Categorical Summary of Epstein-Barr Virus (Viral Load: PCR)

Unit: copies/10⁶PBM cells

Treatment	Visit	N	n	Number of Subjects (%)			
				0-1000	>1000-10000	>10000-100000	>100000
Placebo	X	x		XX (%)	XX (%)	XX (%)	XX (%)
	X	x		XX (%)	XX (%)	XX (%)	XX (%)
	X	x		XX (%)	XX (%)	XX (%)	XX (%)
	.	.					
OTX 9 mg	X	x		XX (%)	XX (%)	XX (%)	XX (%)
	X	x		XX (%)	XX (%)	XX (%)	XX (%)
	X	x		XX (%)	XX (%)	XX (%)	XX (%)
	.	.					
ETC							

Programming Notes : [1] For applicable endpoints, include parameter as either a BY parameter or as first column in the table

Example : EFF_T1
 Protocol : OTX116505
 Population : Safety

Table X.XX
 Summary Statistics (Absolute and Change from Baseline): C-Peptide & Glucose from Mixed Meal Tolerance Test

Parameter: C-peptide Weighted Mean AUC 0-120 mins (nmol/L)

Treatment	N	Visit	Variable	n	Mean	95% Confidence Interval	SD	Min	Median	Max
Placebo	X	Screening	Abs.	X	xxx.x	xxx.x, xxx.x	xx.xx	xxx	xxx	Xxx
		Month 3	Abs.	X	xxx.x	xxx.x, xxx.x	xx.xx	xxx	xxx	Xxx
		XXXX	Chg.	X	xxx.x	xxx.x, xxx.x	xx.xx	xxx	xxx	Xxx
		Month 6	Abs.	X	xxx.x	xxx.x, xxx.x	xx.xx	xxx	xxx	Xxx
		XXXX	Chg.	X	xxx.x	xxx.x, xxx.x	xx.xx	xxx	xxx	Xxx
		XXXX		X	xxx.x	xxx.x, xxx.x	xx.xx	xxx	xxx	Xxx
OTX 9 mg		XXXX		X	xxx.x	xxx.x, xxx.x	xx.xx	xxx	xxx	Xxx

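### Borderline EBV IgM is coded positive at baseline as well as later, so for patients who start borderline SAP Table 2.10 cannot show a rise to clear positivity

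*SAP*

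**What the plan says.** Protocol 5.3.2, Table 7, gives three parameters for EBV reactivation. The serology parameter is a change: "Emergence of IgM for EBV on otherwise EBV-IgG positive patients". Table 8 then combines serology with clinical signs and virology.

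SAP 11.5.3 sets the coding: "Categories (negative, positive) will be derived from absolute IgG and IgM values according to a worst case approach from absolute virus results". Three IgM scales feed one unified class:

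- QUEST index, with a middle band: "0.91 - 1.09 EQUIVOCAL"
- Quest U/ml, with a single cut: "negative: <36 positive: 36 or more"
- BDR, with a middle band: "weakly positive : 20-40"

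The unified IgM column reads "NEGATIVE POSITIVE POSITIVE POSITIVE": only the lowest band is negative. The programming note for Table 2.10 (SAP 11.10.5) applies the same rule. Its shell, titled "Summary of Categorical values of Epstein-Barr Virus (Serology:IgG & IgM", sets each later visit against baseline in four cells: Positive-Positive, Positive-Negative, Negative-Positive and Negative-Negative. Under SAP 5.2, baseline is the last available value before dosing.

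Patients can enter with IgM present. Exclusion 18 (protocol 4.2.2) removes only those with "Positive EBV capsid Ab IgM in absence of a positive EBV EBNA Ab IgG", and exclusion 20 removes those without EBV IgG.

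**The concern.** Calling a doubtful result positive is the cautious choice when the question is how many patients are positive at a visit. For a measure of emergence it is cautious only after baseline. At baseline it takes the patient out of the group in whom emergence can be seen.

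EBV reactivation from Day 21 to Month 24 is a primary safety endpoint. Among the EBV tables in SAP 11.10.5 (2.09 to 2.12), Table 2.10 is the only one that tabulates serology by dose group, and none derives the protocol Table 8 composite. According to the rationale for Amendment 5 (protocol Appendix 8), the Day -1 serology sample was added so that later results would have a baseline for comparison. For a patient with a borderline baseline, the two-level coding discards that comparison.

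**Working it through.** The plan states no figure to reproduce, because this is a coding rule. The check is to enumerate the cases.

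**Step 1: shift cells.** The results are the same for the QUEST index (borderline = equivocal) and the BDR scale (borderline = weakly positive).

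| Baseline to later visit | SAP rule | Borderline negative at baseline only | Borderline negative at every visit |
|---|---|---|---|
| negative to negative | Neg-Neg | Neg-Neg | Neg-Neg |
| negative to borderline | Neg-Pos | Neg-Pos | Neg-Neg |
| negative to positive | Neg-Pos | Neg-Pos | Neg-Pos |
| borderline to negative | Pos-Neg | Neg-Neg | Neg-Neg |
| borderline to borderline | Pos-Pos | Neg-Pos | Neg-Neg |
| borderline to positive | Pos-Pos | Neg-Pos | Neg-Pos |
| positive to negative | Pos-Neg | Pos-Neg | Pos-Neg |
| positive to borderline | Pos-Pos | Pos-Pos | Pos-Neg |
| positive to positive | Pos-Pos | Pos-Pos | Pos-Pos |

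Under the SAP rule, borderline to positive shares a cell with three other cases: borderline unchanged, positive to borderline, and positive unchanged. Negative to positive is shown correctly. On the Quest U/ml scale there is no borderline row, so nothing changes.

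Neither two-level alternative is clean. Recoding at baseline only turns an unchanged borderline value into a new positive. Recoding at every visit loses negative to borderline. Three levels keep all nine cases apart.

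**Step 2: weight of IgM in protocol Table 8.** Take the four serology-positive patterns and set serology to negative:

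- clinical +, serology +, virology +: stays YES
- clinical +, serology +, virology -: changes from YES to NO
- clinical -, serology +, virology +: stays NO
- clinical -, serology +, virology -: stays NO

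Serology is decisive in one pattern of the four.

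**Step 3: size.** In a full active cohort of 8 (protocol 3.1), one patient is 1/8 = 12.5 percentage points. The share q with borderline baseline IgM is not in the documents. Taking q as an assumption, the chance of at least one such patient among 8 is 1 - (1 - q)^8:

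- q = 0.05: 1 - 0.95^8 = 0.34
- q = 0.10: 1 - 0.90^8 = 0.57
- q = 0.20: 1 - 0.80^8 = 0.83
- q = 0.30: 1 - 0.70^8 = 0.94

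These are upper bounds on the chance of a masked rise, since the patient must also become clearly positive.

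**The case against.** The strongest reply is that this concerns one descriptive table and that the data appear elsewhere. Listing 23 covers IgG, IgM and viral load together, Listings 28 and 29 cover serology, and Tables 2.09, 2.11 and 2.12 report mononucleosis-type events and viral load. With about 8 active patients per cohort, a reader could look up a borderline baseline. This stands in large part, although the shell for Listing 23 (OTHER_L12) is not in the available text, so I could not confirm what it displays. A dose-group table of a primary safety component should still not have to be rebuilt from listings.

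Second, the rule also works the other way: negative to borderline is counted as Negative-Positive, which raises the emergent count. That stands. The net direction for the whole table is unknown, so it cannot be said that Table 2.10 understates emergence overall.

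Third, BDR itself labels its middle band weakly positive, so a rise out of that band is arguably not emergence. That stands as a question of interpretation. It is a reason to give the shift its own cell rather than merge it into either neighbour.

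Fourth, a third level does not exist on the Quest U/ml scale. That stands and needs a footnote.

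A reader might also infer that escalation decisions were affected. The documents do not support this: those reviews use the Table 8 assessment, and SAP 2.3 records that stopping criteria had already been met in Cohort 3.

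**Conclusion.** The point holds in a narrow form. For patients whose baseline IgM is equivocal on the QUEST index or weakly positive on the BDR scale, Table 2.10 cannot show a rise to positive, because the worst-case label is applied at baseline, where it is not the worst case for emergence.

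A reader might go further and conclude that IgM emergence defines reactivation and that the plan hides it. The documents do not support that. Table 8 requires clinical signs plus serology or virology, and emergence from a negative baseline is still tabulated.

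Nor can the number affected be stated. The borderline share is not given, the actual size of Cohort 3 is not given, and before Amendment 5 the protocol excluded positive EBV IgM without the EBNA condition, so a single share cannot be assumed for every cohort. The 12.5 points per patient assumes a full cohort of 8. The reading of the unified class column assumes that its flattened order is negative first and positive for the rest, which agrees with the stated worst-case approach.

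**What to change.** In SAP 11.5.3 and shell SAFE_T3, for IgM only:

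- Replace the two-level shift with three levels: negative, equivocal or weakly positive, positive.
- Show borderline to positive as its own cell, and report it beside negative to positive.
- Footnote the number already clearly IgM positive at baseline, in whom emergence cannot occur.
- Footnote that the Quest U/ml scale has no middle level.
- Say which level a BDR value of exactly 40 belongs to. The printed bands overlap there; this did not matter with two levels but does with three.

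Do not recode borderline as negative at baseline only, since unchanged values would then appear as new positives.

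The cost is one SAP line and one shell change, using results already held. The downside is a wider table with sparser cells. The change concerns tabulation only and leaves the protocol's stopping criteria as they are.
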